### 3.3. Tumor Related Endpoints and Definitions

Tumor related endpoints in this study will be based on RECIST v1.1 modified with respect to the definition of what constitutes **progressive disease** (PD) as follows. Any of the following will constitute PD per modified RECIST v1.1:

- Locoregional disease progression per RECIST v1.1 which is subsequently confirmed by pathology. Pathologic confirmation of progression will verify that radiographic changes represent true tumor progression and not radiation effects or non-malignant contrast enhancement.
- Locoregional clinically detectable progression that is confirmed by pathology.
- Surgical removal (salvage) of primary tumor with tumor present on final pathology.
- Salvage neck dissection >20 weeks (140 days) after completion of CRT with tumor present on final pathology.
- Metastatic (distant metastases) disease progression per RECIST v1.1. Confirmation of pathology is recommended unless medically contraindicated or lesion location too high risk for biopsy.

Pathologic evaluation of resected or biopsied specimens must be completed by a trained and medically qualified expert (eg, specialty board certified pathologist).

**Pathologic complete response** is defined as the absence of histologically identifiable residual cancer in any resected specimen.

**Local failure** is defined as residual or recurrent viable tumor on pathologic evaluation from the site of original tumor location. Presence of tumor is required for declaration of a progression event which requires identification of viable tumor cells on final pathology. Tumor reappearing within the initial and immediately adjoining anatomical region of the primary will be considered local recurrence.

**Regional failure** is defined as residual or recurrent viable tumor on pathologic evaluation from the regional lymph node basins (eg, neck nodes). Presence of tumor is required for declaration of a progression event which requires identification of viable tumor cells on final pathology.

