**Distant metastatic disease** is defined as new tumor identified at a site distant from the head and neck anatomic region or draining lymph nodes. Biopsy of any presumed distant metastatic disease is strongly recommended. A solitary, speculated lung mass/nodule is a second primary neoplasm and is not a disease progression event unless proven otherwise by biopsy in a patient with a smoking history. Multiple lung nodules/masses are considered distant metastases from the index cancer and constitute a disease progression event unless proven otherwise by biopsy.

Irradiation of the primary tumor and radiographically enlarged lymph nodes is considered part of the treatment under investigation in this clinical trial and therefore these target lesions remain evaluable lesions for response assessment.

It is expected that the status of the primary tumor is assessed thoroughly at the beginning of the surgical procedure before undertaking nodal dissection. Presence of persistent disease at the primary site, confirmed by frozen section will be considered disease progression.

Neck dissection parameters are described in [Section 3.4](#) and will consist of a selective neck dissection unless a cytologic sampling of the nodes that appear enlarged is negative.

Positive neck specimens removed within 140 days after completion of CRT will be considered part of the initial treatment plan and not considered as failures of initial management; positive specimens upon neck dissection beyond 140 days will be considered regional failures.

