Additional radiological tumor assessments will also be conducted whenever disease progression is suspected (eg, symptomatic deterioration or physical exam findings suggestive of mucosal recurrence). See the [Schedule of Activities](#).

If radiologic imaging shows progressive disease, assigned study treatment should be continued while awaiting pathologic confirmation of disease progression per modified RECIST v1.1 unless the patient is clinically unstable and/or requires an urgent alternative intervention (eg, decompression of a spinal cord compression). All locoregional disease recurrence or progression must be pathologically confirmed (see [Appendix 3](#)). The date of progression will be the date of the radiographic evaluation that showed progression which was subsequently confirmed by pathology.

All radiographic images will be collected and stored for possible future objective verification by an independent third-party core imaging laboratory (central review) as described in the Study Manual. In addition any photographs of clinical progression concerns warranting biopsy will also be collected for potential future review.

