### **9.3.1. Analysis of the Primary Endpoint**

PFS is defined as the time from the date of randomization to the date of the first documentation of objective PD per modified RECIST v1.1 or death due to any cause, whichever occurs first.

The following will be considered events in the analysis of PFS:

- Death due to any cause;

- Locoregional disease progression per RECIST v1.1 which is subsequently confirmed by pathology;
- Locoregional clinically detectable progression that is confirmed by pathology;
- Surgical removal (salvage) of primary tumor with tumor present on final pathology;
- Salvage neck dissection >20 weeks (140 days) after completion of SOC CRT with tumor present on final pathology;
- Metastatic (distant metastases) disease progression per RECIST v1.1.

For the primary analysis, PFS data will be censored on the date of the last adequate tumor assessment for patients who do not have an event (PD per modified RECIST v1.1 or death); the analysis will consider any PD per modified RECIST v1.1 or death as an event regardless of the number of prior missing tumor assessments or timing of the event with respect to initiation of anti-cancer therapy.

The primary analysis of PFS will be performed based on the FAS. A stratified log-rank test (1-sided) stratified by randomization stratification factors will be used at the interim and/or final analyses with the overall significance level preserved at 0.025 (1-sided). PFS times associated with each treatment arm will be summarized using the Kaplan-Meier method and displayed graphically where appropriate. CIs for the 25th, 50th, and 75th percentiles will be reported. The stratified Cox proportional hazards model will be fitted to compute the treatment hazard ratio and the corresponding 95% CI.

A sensitivity analysis for PFS will be performed using the methodology outlined for the primary analysis of PFS above but defining PD as per standard RECIST v1.1. Summary of discordance of PD (event and timing) as well as reasons for discordance between assessment of PFS per modified RECIST v1.1 and standard RECIST v1.1 will be provided for each treatment arm.

PFS based on modified RECIST v1.1 will also be evaluated based on the per-protocol analysis set as a sensitivity analysis using the methodology outlined for the primary analysis of PFS.

Other sensitivity analyses will be pre-specified in the SAP.

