### **9.3.2.7. Neck Dissection**

The rate of neck dissection on each treatment arm will be estimated by dividing the number of patients with neck dissection recorded from randomization until PD per modified RECIST v1.1 or death due to any cause by the number of patients randomized to the respective treatment arm. The corresponding exact 2-sided 95% CIs will be provided by treatment arm.

The rate of pathologically-positive neck dissection and rate of pathologically-negative neck dissection will be analyzed in the same way as the rate of neck dissection.

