**Distant metastatic disease** is defined as new tumor identified at a site distant from the head and neck anatomic region or draining lymph nodes. Biopsy of any presumed distant metastatic disease is strongly recommended. A solitary, speculated lung mass/nodule is a second primary neoplasm and is not a disease progression event unless proven otherwise by biopsy in a patient with a smoking history. Multiple lung nodules/masses are considered distant metastases from the index cancer and constitutes a disease progression event unless proven otherwise by biopsy.

Irradiation of the primary tumor and radiographically enlarged lymph nodes is considered part of the treatment under investigation in this clinical trial and therefore these target lesions remain evaluable lesions for response assessment.

It is expected that the status of the primary tumor is assessed thoroughly at the beginning of the surgical procedure before undertaking nodal dissection. Presence of persistent disease at the primary site, confirmed by frozen section will be considered disease progression.

Neck dissection parameters are described in Section 3.4 of the B9991016 protocol and will consist of a selective neck dissection unless a cytologic sampling of the nodes that appear enlarged is negative. Positive neck specimens removed within 140 days after completion of CRT will be considered part of the initial treatment plan and not considered as failures of initial management; positive specimens upon neck dissection beyond 140 days will be considered regional failures.

Progression-Free Survival (PFS) is defined as the time from the date of randomization to the date of the first documentation of PD or death due to any cause, whichever occurs first. For example, the date of first documentation of PD when there is locoregional PD per RECIST v1.1 which is subsequently confirmed by pathology, will be the date of the locoregional PD per RECIST v1.1 rather than the date of pathology confirmation.

PFS data will be censored on the date of the last adequate tumor assessment or clinical evaluation for patients who do not have an event (PD or death); the analysis will consider any PD or death as an event regardless of the number of prior missing tumor assessments or clinical evaluations or timing of the event with respect to initiation of subsequent anti-cancer therapy.

The censoring and event date options to be considered for the PFS and DR analysis are presented in Table 9.

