#### 6.2.2.6. Neck dissection

A patient who had neck dissection can be identified by the “Surgery Details –Salvage Surgery Neck” eCRF. If the box “Yes” was checked for the question “Was neck dissection performed as expected per protocol?”, the patient had a neck dissection.

The rate of neck dissection on each treatment arm will be estimated by dividing the number of patients with neck dissection recorded from randomization until PD per modified RECIST v1.1 or death due to any cause by the number of patients randomized to the respective treatment arm. The corresponding exact 2-sided 95% CIs will be provided by treatment arm.

The rate of pathologically-positive neck dissection and rate of pathologically-negative neck dissection will be summarized using the same methodology as for the rate of neck dissection.

The final pathology of neck dissection (positive or negative) can be identified from the “Outcome” field in the “Pathology Details” eCRF with “Lesion number” and “Date of sample” matching “Lesion number” and “Date of neck dissection” in the “Surgery Details – Salvage Surgery Neck” eCRF.

- Positive pathology includes the following outcomes from the “Pathology Details” eCRF: (1) live tumor cells present, or (2) 10% or greater vital tumor tissues.
- Negative pathology includes the remaining outcomes: (3) no live tumor cells present, (4) complete tumor regression, no evidence of vital tumor tissues, (5) less than 10% vital tumor tissue, or (6) not consistent with disease under study.

The outcome of the pre-surgery biopsy sample (positive or negative) can be identified from the “Outcome of biopsy” field in the “Biopsy Sample Details” eCRF with “Lesion number” and “Date of biopsy sample” matching “Lesion number” and “Date of pre-surgery biopsy sample” in the “Surgery Details –Salvage Surgery Neck” eCRF.

The positive and negative predictive values (PPV and NPV respectively) of the biopsy to the final pathology will be calculated based on the subset of patients who had neck dissection and a pre-surgery biopsy sample (matching lesion number and date).

- $PPV = TP / (TP + FP)$  where TP is the number of lesions with true positive pre-surgery biopsy (pre-surgery biopsy positive and positive pathology) and FP is the number of lesions with false positive pre-surgery biopsy (pre-surgery biopsy positive and negative pathology).

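### The neck-dissection rates stop at PD, so whether a late dissection is counted can depend on the pathology result being reported

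*Protocol*

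**What the plan says.** Protocol 9.3.2.7 divides the "number of patients with neck dissection recorded from randomization until PD per modified RECIST v1.1 or death due to any cause" by the number randomized to the arm, with an exact 95% CI per arm. It adds: "The rate of pathologically-positive neck dissection and rate of pathologically-negative neck dissection will be analyzed in the same way". SAP 6.2.2.6 repeats the window ("number of patients with neck dissection recorded from randomization until PD per modified RECIST").

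On dating, Protocol 7.8 says of locoregional progression: "The date of progression will be the date of the radiographic evaluation that showed progression which was subsequently confirmed by pathology". SAP 6.1.1.1 agrees: for locoregional PD seen under RECIST and later confirmed by pathology, the first documentation of PD "will be the date of the locoregional PD per RECIST v1.1 rather than the date of pathology confirmation".

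On what a positive specimen means, Protocol 3.3 draws a line at 140 days. Early: "Positive neck specimens removed within 140 days after completion of CRT will be considered part of the initial treatment plan", so there is no PD. Late: "Salvage neck dissection >20 weeks (140 days) after completion of CRT with tumor present on final pathology" is a PD event in its own right, and Protocol 9.3.1 lists it among the PFS events. A late specimen without tumor is not PD under any of the listed routes.

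**The concern.** Each rule is reasonable alone. Together they make the counting window end at a date that is settled by the pathology of the operation being counted, or by a biopsy taken just before it. Two patients with the same suspicious scan and the same operation can be treated differently: the positive one drops out and the negative one stays in.

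Neck dissection is a listed secondary antitumor-activity endpoint. The operations at risk of being dropped are tumor-positive salvage dissections for nodal recurrence, which better nodal control should prevent. The positive and negative rates would also be read side by side although they capture late operations differently.

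**Working it through.** **No figure to reproduce.** Neither document gives an expected dissection rate, a precision target or power for this endpoint. The check is of event order, followed by a labeled illustration.

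**Calendar** (Protocol 3.3 and 7.8). The cutoff is 20 × 7 = 140 days after CRT. The first post-CRT assessment is at 12 × 7 = 84 days (up to 91 with the one-week allowance). The next is at (12 + 16) × 7 = 196 days, or 189 at the earliest. Any nodal recurrence first seen on a scheduled scan after the week-12 one is therefore already past day 140.

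**Event order for a dissection beyond 140 days**

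| Route | PD date | Counted? |
|---|---|---|
| A. Scan shows RECIST progression; the specimen is the first positive pathology | Scan, before surgery | No |
| B. Progression confirmed by positive biopsy before surgery | Biopsy date or earlier | No |
| C. No earlier documented progression; specimen positive | The dissection is the PD event | Only if the window includes the PD day, which is not stated |
| D. Same scan as A; specimen negative | None from this scan | Yes, in total and negative rates |

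A and D differ only in the pathology result. B would be excluded even if PD were dated at pathology. C is a gap in wording.

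**Illustration.** The only documented input is about 640 / 2 = 320 patients per arm. Everything else is assumed: 24 dissections within 140 days (12 positive, 12 negative), L late dissections, a share q of these positive, and a share k of the late positives with PD before surgery.

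- All dissections: (24 + L) / 320; counted: (24 + L − kqL) / 320
- All positive: (12 + qL) / 320; counted: (12 + qL − kqL) / 320
- Negative, either way: (12 + (1 − q)L) / 320

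| L | q | k | Total: all → counted | Positive: all → counted | Negative |
|---|---|---|---|---|---|
| 8 | 0.5 | 1 | 32/320 = 10.0% → 28/320 = 8.75% | 16/320 = 5.0% → 12/320 = 3.75% | 16/320 = 5.0% |
| 16 | 0.75 | 0.5 | 40/320 = 12.5% → 34/320 = 10.6% | 24/320 = 7.5% → 18/320 = 5.6% | 16/320 = 5.0% |
| 16 | 0.75 | 1 | 40/320 = 12.5% → 28/320 = 8.75% | 24/320 = 7.5% → 12/320 = 3.75% | 16/320 = 5.0% |
| 32 | 0.75 | 1 | 56/320 = 17.5% → 32/320 = 10.0% | 36/320 = 11.25% → 12/320 = 3.75% | 20/320 = 6.25% |

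With k = 0 nothing is lost. With k = 1 the counted positive rate always falls to the assumed early positives, 12/320. The negative rate never moves.

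**The case against.** The best defense is that stopping at PD is deliberate. Pathologic complete response and objective response in Protocol 9.3.2 use the same window, the protocol treats dissection within 140 days as initial management, and SAP 6.2.2.6 identifies patients through an eCRF item on whether the dissection was done as the protocol expects. This has some force, but the written window is PD and not 140 days. Late tumor-negative dissections can therefore enter an endpoint supposedly limited to planned surgery, and the text delivers neither a planned-only nor an all-dissections rate.

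A reader might infer that a difference between arms in salvage surgery would disappear from the report. The documents do not support that. SAP 6.1.1.1 tabulates PD subtypes by arm, including late positive salvage dissection. Locoregional failure in SAP 6.2.2.4 includes that event and confirmed nodal recurrence, and is compared by stratified log-rank test and Cox model. SAP 6.5.5 tabulates anti-cancer therapy after discontinuation by type, including follow-up surgery. The cover is only partial: a recurrence first called on a scan may be filed under the radiographic subtype, and locoregional failure counts recurrences and deaths, not operations.

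A reader might also blame scan-dating alone. Route B shows otherwise, and a persistent node that never met RECIST progression has no scan PD date to go back to. Finally, dissection is not planned where nodal cytology is negative (Protocol 3.4), which may keep late negative operations few and the positive/negative asymmetry small.

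**Conclusion.** The point holds in limited form. Nothing elsewhere in either document removes the dependence of inclusion on pathology. The error runs one way: late positive dissections can be lost from the total and positive rates, while the negative rate is untouched.

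Its size cannot be taken from the documents. It runs from zero (every late positive dissection is the first PD event and the window includes that day) to all late positives (PD always precedes surgery). In the illustration the largest loss shown is 7.5 percentage points (17.5% to 10.0%), under assumed inputs. It would be wrong to infer that all late salvage is lost: the dissection can itself be the PD event, and positive dissections within 140 days stay in.

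The endpoint is descriptive, so type I error and power are not affected. What is at stake is the meaning of the reported rates and of their positive/negative split. This is worth correcting before the analysis but does not threaten the trial's main conclusions.

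**What to change.** In Protocol 9.3.2.7 and SAP 6.2.2.6:

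1. Report two rates by arm: (a) dissections within 140 days of CRT completion and (b) later salvage dissections. Split each by positive and negative pathology.
2. State that the dissection that confirms or treats the first nodal PD event is counted in (b), whatever PD date is assigned.
3. Report dissections after that one as supportive only, as far as they were collected.

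Counting every dissection to death or last follow-up as the main rate would go too far. Protocol 3.1 continues tumor assessments until PD and limits long-term follow-up to survival and new systemic anticancer treatment. A follow-up surgery eCRF page exists, but nothing shows that neck-surgery and matched pathology pages are completed systematically after PD.

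The cost is a wording change in both documents and one extra table split. SAP 6.2.2.6 already matches surgery and pathology records by lesion number and date. The total rate will be somewhat higher than under the present rule, and capture of surgery after PD may be incomplete, which the table should say.

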### **9.3.2.8. Patient-Reported Outcomes**

The FAS will be used for the PRO analysis.

NCCN-FHNSI-22 and EQ-5D-5L, will be scored according to their respective validation papers and user's guides. For the EQ-5D-5L, utility scores will be calculated using the published weights (tariffs) for the United Kingdom (UK). Specific country weights may be applied for country specific analyses as needed.

Summary statistics (mean and standard deviation [SD], median, range) of absolute scores will be reported for the total and subscales of the FHNSI-22, and the utility and VAS scores of the EQ-5D-5L. The mean change of absolute scores from baseline (and 95% CI) will also be reported. Line charts depicting the means and mean changes of items and subscales over time will be provided for each treatment arm.

Symptoms of disease will be assessed using the DRS-P subscale of the NCCN-FHNSI-22 with a focus on the single item 'I can swallow easily and naturally'. HRQoL will be assessed using the FWB subscale of the NCCN-FHNSI-22 and also the EQ-5D-5L.

Treatment arms will be compared using percent of patients with improvement in swallowing, defined as a 1-point increase on the 5-point Likert scale maintained for 2 consecutive assessments, in the single 'swallowing' item of the FHNSI-22. A chi-square test will be used for the analysis including patients in the FAS with a baseline score and at least one post-baseline assessment.

Treatments arms will be compared based on time to deterioration (TTD) of 1) HRQoL, 2) disease-related symptoms-physical, and 3) 'swallowing'. TTD is defined as the time from randomization to deterioration where deterioration is defined, respectively, as 1) a 3 point decrease on the FWB scale for health-related quality of life (HRQoL), 2) a 3 point decrease on the DRS-P for symptoms of disease, and 3) a 1 point decrease on the 'swallowing' item of the FHNSI-22, in two consecutive assessments. The time to event will be calculated using

the date of the baseline assessment and the date of first of the two consecutive assessments use to identify the event. Note that a decline in FWB subscale of the FHNSI-22 represents a worsening in HRQoL. A decline in DRS-P score represents an increase in physical symptoms of disease. A decline in the 'swallowing' item score represents a decrease in the ability to swallow naturally and easily.

Patients will be censored at the last time when they completed a PRO assessment if they have not deteriorated prior to death, lost to follow-up or the last scheduled PRO assessment.

TTD associated with each treatment arm will be summarized using the Kaplan-Meier method and displayed graphically where appropriate. CIs for the 25th, 50th, and 75th percentiles will be reported. The Cox proportional hazards model will be fitted to compute the treatment hazard ratios and the corresponding 95% CIs.

Treatment arms will be compared based on mean scores of the FHNSI-22 total, subscales and the EQ-5D-5L utility and VAS scores obtained from repeated measures, mixed-effects regression models that contain the baseline score as a covariate. Other exploratory PRO analyses may be performed subsequently.

